5.6.7 Retention Strategies to Ensure Follow-up

We will leverage the long-established retention strategies at the research site to retain participants in this study. Participants will be closely tracked by a dedicated experienced team of dedicated staff to minimize missed visits and loss to follow-up at both the Uganda and Malawi sites. This will be done primarily calling participants by mobile phone and reminding/re-scheduling visits as appropriate. Our staff also works with home locators to conduct a home visit as needed. This approach has proven highly successful at the two sites with 2-year retention rates >95% at prior trials in the Uganda and Malawi sites.

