Sample sizes for Aims 1, 2, and 3. Sample size considerations are based on having sufficient power to discriminate known groups based on the proximal factor of HIV status/exposure, a key factor for Aim 1. The preliminary data from PROMISE ND study indicate that the differences in the composite neurodevelopmental score (the Mullen Scale of Early Learning) between HEU and HUU cohorts corresponded to the effect size of Cohen's $d=0.26$ (difference between the means of 0.26 of the standard deviation). To detect this difference between HUU and HEU cohorts, $n=240$ per cohort is needed for power ≥ 0.80 in two-tailed tests at 0.05 level of significance. Based on the preliminary data, the effect size d for comparisons of the HIV vs HUU or HEU is at least 0.31. This can be detected with power ≥ 0.80 with $n=120$ in the HIV group. Therefore, the proposed total sample size for both sites combined is $n=240$ HUU; $n=240$ HEU; and $n=120$ for HIV+ children.

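### Power for the HIV+ contrasts is about 0.79 rather than at least 0.80 at the stated minimum effect of d = 0.31, and the sample-size text makes no allowance for loss by 7 months

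*Combined protocol and SAP*

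**What the plan says.** The paragraph on sample sizes for Aims 1, 2 and 3 in section 7.1.2 sizes the study to discriminate groups known to differ by HIV status or exposure.

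- **HEU versus HUU:** the effect is a "difference between the means of 0.26 of the standard deviation", and 240 children per cohort are said to be needed for power of at least 0.80 "in two-tailed tests at 0.05 level of significance".
- **HIV+ versus HUU or HEU:** the plan states that the effect size for "comparisons of the HIV vs HUU or HEU is at least 0.31", and then: "This can be detected with power ≥ 0.80 with $n=120$ in the HIV group".

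The totals that follow are 240 HUU, 240 HEU and 120 HIV+ children. Section 5.4 sets exactly these numbers as enrolment targets.

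The analyses in section 7.1.2 use measurements at intake, 1 month and 7 months, as does the primary outcome in section 5.3. The sample-size paragraph does not mention loss to follow-up. The only retention figure is in section 5.6.7, which reports "2-year retention rates >95% at prior trials in the Uganda and Malawi sites".

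**The concern.** Two things stand out. First, the HIV+ claim is written as an inequality at a named minimum effect, and the inequality is not quite met at that effect. Second, the paragraph goes straight from the number required to the number enrolled, although it covers aims whose data run to 7 months. If enrolment only just reaches the target power, or falls slightly short, any loss takes follow-up comparisons below it.

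What is at stake is how a null result is read. Someone interpreting a non-significant HIV+ contrast at 7 months would take it that an effect of 0.31 had at least an 80% chance of detection. The actual chance is somewhat lower.

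**Working it through.** **Inputs from section 7.1.2.** d = 0.31 for HIV+ versus HUU or HEU, with 120 versus 240 children. d = 0.26 for HEU versus HUU, with 240 versus 240. Two-sided alpha is 0.05; it is stated for HEU versus HUU and assumed to carry over to the HIV+ comparisons.

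**Method.** Two-sample comparison of means on the standardised scale (SD = 1). The noncentrality is d / √(1/n1 + 1/n2). Power is taken from the noncentral t distribution, with the normal approximation Φ(noncentrality − 1.96) as a check.

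**1. HEU versus HUU at full enrolment.** Noncentrality = 0.26 / √(2/240) = 0.26 / 0.0913 = 2.848. Power is 0.811 (t) or 0.813 (normal). The plan's statement is met. The smallest group size that gives 0.80 is 234 per cohort (power 0.801), so 240 leaves 6 children per cohort to spare: 6/240 = 2.5%.

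**2. HIV+ versus HUU or HEU at full enrolment.** Noncentrality = 0.31 / √(1/120 + 1/240) = 0.31 / 0.1118 = 2.773. Power is 0.790 (t) or 0.792 (normal). The stated value is at least 0.80, so the gap is about one percentage point.

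**3. What would give 0.80 for the HIV+ contrast.**
- With 120 versus 240, d must be 0.314 (t) or 0.313 (normal).
- With d = 0.31 and 240 comparators, 125 HIV+ children (t, power 0.800) or 124 (normal, power 0.800).

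**4. Sensitivity to rounding of d.** A value of 0.3149 still prints as 0.31 and gives 0.802. A value of 0.305 also prints as 0.31 and gives 0.777.

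**5. Loss to follow-up.** The plan states no rate, so the rates below are assumptions, applied equally to all cohorts. Section 5.6.7 implies less than 5% loss over 24 months in prior trials. Spread evenly, that is under 5% × 7/24 ≈ 1.5% by 7 months. The 5% row is therefore cautious, and the 10% row has no source in the documents.

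| Assumed loss | HIV+ / HUU / HEU remaining | Power, HIV+ contrast (d = 0.31) | Power, HEU vs HUU (d = 0.26) |
|---|---|---|---|
| 0% | 120 / 240 / 240 | 0.790 | 0.811 |
| 1.5% | 118 / 236 / 236 | 0.783 | 0.805 |
| 5% | 114 / 228 / 228 | 0.769 | 0.791 |
| 10% | 108 / 216 / 216 | 0.746 | 0.769 |

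All entries are t-based and treat the follow-up analysis as a simple two-group comparison of the children who remain. At 5% loss the detectable d at 0.80 power is 0.322 for the HIV+ contrasts and 0.263 for HEU versus HUU.

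**The case against.** The case for leaving the text alone has several parts.

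- **The gap at intake is at rounding level.** A power of 0.79 is commonly reported as 80%, and the plan gives 0.31 as a minimum to two decimals. If the unrounded figure is about 0.314 or more, the statement is correct as written. This stands as a limit on the size of the point. It does not remove it: the plan says at least 0.80 at that floor, the unrounded value is not given, and rounding could equally hide a smaller effect.
- **The sizing basis is available at intake.** Discrimination by HIV status can be tested at baseline, where later loss does not matter. This stands for intake comparisons. The paragraph nevertheless claims to size Aims 1, 2 and 3, which use later measurements.
- **The planned models are not two-sample t-tests.** Linear mixed models keep children with incomplete series, and covariate adjustment may add precision. For illustration, covariates unrelated to group that explain 3% of outcome variance would raise the effective d to 0.31/√0.97 = 0.315 and power to about 0.80. With confounded covariates the gain could be smaller or reversed. This stands as a reason to treat the follow-up figures as approximate; the plan's own calculation takes no credit for either feature.

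Two stronger readings are tempting, and the documents do not support them. A reader might infer that the protocol plans on 5% loss in this study. Section 5.6.7 only reports more than 95% retention over two years in prior trials. A reader might also infer that HEU versus HUU is underpowered at follow-up on the plan's own figures. That contrast keeps 0.80 up to about 2.5% loss, and the prior-trial rate scaled to 7 months is below that.

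**Conclusion.** The point holds and is minor. At exactly d = 0.31, with two-sided alpha 0.05, 120 versus 240 children give power of about 0.79, one percentage point below the stated minimum and with nothing in reserve. It does not follow that both HIV+ contrasts fall short, because 0.31 is a lower bound and either true effect may be larger.

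The missing allowance for loss is a separate omission. Its effect is modest if retention matches prior trials: about 0.78 for the HIV+ contrasts and 0.80 for HEU versus HUU at 1.5% loss. At 5% loss the figures are about 0.77 and 0.79. These follow-up values assume equal loss across cohorts and a simple two-group comparison, so they approximate the planned mixed models. Nothing here calls for a different sample size or analysis.

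**What to change.** Keep 240, 240 and 120, and revise the sample-size paragraph in section 7.1.2 as follows.

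1. State power at intake as about 0.79 for HIV+ versus HUU or HEU at d = 0.31 (detectable d about 0.314 at 0.80 power), and 0.81 for HEU versus HUU at d = 0.26. If an unrounded effect of about 0.314 or more was used for the HIV+ contrasts, give that value instead.
2. Say that the two-sided 0.05 level also applies to the HIV+ comparisons.
3. State an assumed loss by 7 months, with its basis, and the resulting power. At 5%, a simple comparison gives about 0.77 and 0.79; note that the mixed models can use incomplete series.

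The cost is wording only. The stated power becomes slightly less favourable, and no additional children are needed.

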8.0 ETHICAL AND REGULATORY CONSIDERATIONS

The study will be conducted in compliance with country-specific regulatory requirements for each of the participating sites and strictly follow GCP/HSP requirements. Written informed consent will be obtained in the local language of the mother after explanation of the purpose of the study, the procedures to be followed and the risks and benefits of participation; and answering the women's questions. A copy of the consent forms will be given to the subject unless he declines to take them. Every attempt will be made by study staff to ensure privacy and preserve confidentiality of study participants. All clinical study staff involved in the study is trained on GCP/HSP and their certificates will be reviewed on an annual basis

to ensure training compliance. All study records will be kept in a secured area with limited access. All computer entry and networking programs will be performed with coded numbers only. All laboratory specimen reports, and other records that are transferred or transmitted off-site will be identified by a coded number to maintain subject confidentiality.

8.1 Human Subjects Protection

The Culture-specific neurodevelopment assessment of HIV-affected children study will enroll HEU and HUU children and their caregivers from the PROMISE ND study at the Blantyre Malawi and MU-JHU Uganda Kampala Clinical Research Sites (CRSs); and HIV infected children of similar age and from the IMPAACT P1104s study and health clinics from which the CRSs enroll. This study's protocol will follow the Human Subjects requirements as summarized below. The proposed principal investigators as well as all key co-investigators are all highly qualified researchers and are in compliance with the Office for Human Research Protection (OHRP) requirement concerning protection of human research participants (HSP/GCP). All personnel working on this study have training on the protection of human research participants to ensure compliance and maintain confidentiality of study participants and their data.

8.2 Potential Risks

Distress for research participants: Although neuropsychological assessments bear no potential harm on participants, they can be long and tedious for some children. We will be particularly attentive to the child's needs, providing frequent breaks and refreshments as needed so the child is not unduly stressed. Training of our testing staff includes sensitization to each child's needs and the potential for stress and frustration reactions derived from testing. In case any participant becomes distressed at any point during the assessments, testing staff will suspend the test and assess the need for referral to psychological support available at each participating site in Uganda and Malawi. However, sections of the neuropsychological assessments involve game-like tasks that can be entertaining to the participant. Furthermore, sections of the testing (Cogstate and Brain Powered Games) are carried out on an appealing electronic console (i.e. tablet) popular among children, potentially entertaining the participant.

8.3 Adequacy of Human Subjects Protection against Risks

Recruitment and Informed consent: The subject population for this proposal will consist of 600 children roughly equally divided between males and females. These are Ugandan and Malawian children 5-14 years of age at study initiation who live in Uganda or Malawi. The caregiver may or may not be the biological parent of the study children but will be an adult who has a primary role in the child's growth and protection. Study staff already known to our previous R01 cohort participants (un-exposed - HUU, un-infected and exposed-uninfected children - HEU) will make the initial contact through clinic visits and telephone calls. HIV infected children from HIV care clinics at both sites and PROMISE ND studies (HEU, HUU) in Uganda and Malawi will be invited to participate using the same mechanism. Informed and signed consent will be obtained from all caregivers who will provide consent for their child to participate, while child assent will be obtained for children 7 years and older according to local regulations. Information will be provided and consent forms given in either English or one of the local languages (Luganda, Chichewa) they comprehend with the consent being administered in the language of their choice. The consent form will be read aloud and explained to the caregivers, who will then sign the consent or provide a thumb-print. A copy of the consent will be given to the caregivers. An assessment of understanding will be conducted for all participants after consent reading by an independent person to ensure that the potential participants understand what they are consenting for.

All centers participating in this study will have active institutional review board (IRB) approved protocols and maintain IRB and all other necessary approvals for this study throughout its conduct.

8.4 Potential Risks Protection against Breach of Confidentiality of Study Data

All participants enrolled into the study will be assigned a unique PTID. The PTID number will be used for identification purposes on all laboratory specimens, evaluation forms, and reports retained in the research records and generated in the protocol database. A list linking the subjects' names with PTID numbers will be stored at the clinical site under double lock and key in a secure area accessible only to limited staff on the study. All study records will be stored in secure areas with locks.

8.5 Consideration of Potential Benefits of Proposed Research

Children living in poverty and/or affected by HIV/AIDS are at risk, either directly or indirectly, of compromised care giving, economic impoverishment, and poorer overall quality of home environment throughout the sensitive period of childhood development. This could compound cognitive and psychosocial deficits that can affect a child's ability to fully benefit from schooling and could limit the child in other aspects of life. These children may have difficulty with learning and maintaining concentration, which will in turn affect their school performance, subsequent educational opportunities, and future economic prospects. Intervening to prevent cognitive deficits from the direct or indirect effects of poverty and stressful environmental conditions on the child and family requires understanding the impact of these on caregiving quality and overall quality of home environment and developmental milieu.

Our study will provide evidence for the usefulness of an innovative neurodevelopmental assessment for school-age children that could be of great importance to families in poverty-stricken countries such as Uganda and Malawi. In these countries, more than a third of all inhabitants live under the poverty line, with about four million children under the age of five being the primary victims of this deplorable economic situation. Given the scope of the humanitarian need of such children globally, our research could be of great benefit in terms of providing evidence in support of strategic and sustainable neurodevelopment assessments during childhood for children living in poverty and affected by HIV/AIDS.

8.6 Staff Training on Protection of Human Subjects

All research staff will be trained on GCP and HSP. Research health visitors will work with participants to establish other contact persons who may be contacted in case the health visitor is unable to reach the study

participant. The two CRS regulatory staff will ensure compliance with all GCP/HSP requirements.

8.7 Ensuring Participant Confidentiality

All efforts will be made not to release personally identifying information to non-study staff except to monitors, the IRBs and the sponsor as necessary. Clinically obtained evaluations will be identified by PTIDs. Any data sent to collaborating institutions will be only transmitted using unique PTIDs on the case report forms. The site investigator will make study records and pertinent records available for inspection by the local IRB, site monitors, the NIH, the OHRP, or the sponsor for confirmation of study data. This study is protected by a Certificate of Confidentiality provided by the NIH.

8.8 Safety Monitoring Plan

Site investigators (Investigators of Record or IoRs /designees) are responsible for continuous close safety monitoring of study participants, and for alerting the Protocol Team if unexpected concerns arise.

Both MU-JHU in Uganda and JHP in Malawi presently sponsor a Health Ethics Committee made up of a multidisciplinary team including representatives from the community and faculty members (medicine, law, economics, nursing, and administration). The Committee is responsible for the approval of all research projects carried out in the in these institutions, and of projects with external investigators collaborating with them. The Committee will be responsible for reviewing the project protocol and the consent forms, ensuring protection of human subjects' rights. The Committee will ensure fulfillment of the ethical principles of the research project and be available to research subjects in case of any doubt or concern with the project. The MSU Office of Clinical and Translational Research is also committed to supporting us in the formation and support of our DSMB.

8.9 Adverse Event Reporting

Cognitive/motor developmental and cognitive testing of children has clear potential benefits and no definable risk. All standards of care for study children in the event of illness will be observed according to Ugandan and Malawian Ministry of Health recommended hospital protocols for such illnesses.

Adverse event management plan: Our project field trainers in the Uganda and Malawi study sites will have clinical officers available who will be able to assess medical need during their assessment visits at the office. They will also be equipped to administer care and medication for most opportunistic infections and first aid care for any accidental injuries that subjects are likely to encounter. The Uganda staff will also notify [name] (Co-I) by mobile phone for medical concerns and consultation while the Malawi staff will do so with [name] (Co-I). Both Drs. [name] and [name] are experienced clinical biomedical scientists who can coordinate our clinical care support for the study children. If medical follow-up is needed, our medical staff will make the appropriate referrals.

Study participants will be provided instructions for contacting the study site to report any untoward occurrences they may experience. In cases of potentially life-threatening events, participants will be instructed to seek immediate emergency care. Where feasible and medically appropriate, participants will be encouraged to seek evaluation at the study clinic. With appropriate permission of the participant, whenever possible, records from non-study medical providers related to untoward medical occurrences will be obtained and required data elements will be recorded on study CRFs. Study site staff will document in source documents all AEs reported by or observed in enrolled study participants regardless of severity. The reports will also include experiences of social harm.

8.10 Social Harms Reporting

Although study sites will make every effort to protect participant privacy and confidentiality, it is possible that participants' involvement in the Culture-specific neurodevelopment assessment of HIV-affected children study could

become known to others and that social harms may result. For example, participants could be treated unfairly, or could have problems being accepted by their families, partners and/or communities if their participation in the Culture-specific neurodevelopment assessment of HIV-affected children study were to be inadvertently disclosed. Social harms that are judged by the site IoR /designee to be serious or unexpected will be reported promptly to the SMC and responsible site ECs/IRBs according to their individual requirements. In the event that a participant reports social harm, every effort is made

By study staff to provide appropriate care and counseling to the participant, and/or referral to appropriate resources for the safety of the participant as needed. Each site will provide such care and counseling as defined in the site SOPs. While maintaining participant confidentiality, study sites may engage their community advisory boards (CABs) in exploring the social context surrounding instances of social harm.

8.11 Regulatory Requirements

Site IoRs /designees will submit AE information and other relevant safety information in accordance with local regulatory agencies' including IRB/ethical committees, other local authorities and sponsor requirements.

9.0 PLANNED TIME LINES

The Culture-specific neurodevelopment assessment of HIV-affected children Study is planned to run for 5 years including obtaining IRB approvals, data analysis, BPG development and deployment and report writing. Data cleaning will be ongoing and data analyses will also occur during year 5 with presentation of findings at international and local meetings and to the local stake holders (e.g. MOH). These timelines are detailed below regarding the various activities over 5 years.

Timeline of the Project	Year 1				Year 2				Year 3				Year 4				Year 5			
Quarters:	1	2	3	4	1	2	3	4	1	2	3	4	1	2	3	4	1	2	3	4
IRB approval	X	X																		
Update manuals: hire/train	X	X	X	X																
Enhance BPG software	X	X	X	X																
Enroll subjects: deliver					X	X	X	X	X	X										
Deliver BPG training, conduct						X	X	X	X	X	X	X	X	X						
Mobile network deployment													X	X	X	X	X	X		
Data management									X	X	X	X	X	X	X	X				
Data analysis										X	X	X	X	X	X	X	X			
Annual/final reports			X			X			X					X					X	
Dissemination of results																		X	X	

10.0 PUBLIC HEALTH IMPACT

BPG (Brain Powered Games) is designed as a scalable open-access cognitive rehabilitation intervention for HIV-positive school-age children living in Sub-Saharan Africa; used to train a child's fine motor skills, monitoring/attention, visual/auditory working memory, and spatial navigation ability. We will develop an additional game for executive function training, and then test whether BPG games cognitive assessment data gathered as at-risk children play with BPG, can provide a more sensitive measure of a child's developing brain. The Village Builder EF game will be prosocial, non-violent, non-threatening, and will draw from the African village context in a positive and familiar manner. We will pilot the same features with comparable children at the study sites and use their evaluative comments and observed engagement with the new game so further refine and finalize the Village Builder game features, as was the case with the development of African BPG with both

children in Blantyre, Malawi and in Kayunga, Uganda.^{1,71}

Both the existing Africa BPG package and the new Village Builder EF games will be used to demonstrate that a child's performance on a neurocognitive "stress test"; involving game training with an app on a computer tablet, will better characterize integrity of brain/behavior function as compared to performance outcomes from traditional one-time cognitive testing sessions.

